### 3.1 Procedures Overview

The present proposal aimed to adapt, pilot and examine the credibility, acceptability, adherence and feasibility of the GetActive and GetActive with Fitbit adapted for older adults with MCI or memory-related problems (MRP) (*Active Brains and Active Brains with Fitbit*). We have already developed the GetActive and GetActive-Fitbit which are adapted for the specific needs of patients with chronic pain, but not for older adults with MCI or MRP, who are currently excluded from the R34 study. We now aim to compare *Active Brains-Fitbit* vs an attention placebo control (HEP) in a pilot randomized control trial. Our goal is to compare the credibility, feasibility, usability and adherence between the two programs, *Active Brains-Fitbit* and the HEP, as well as all study procedures in preparation for an efficacy trial. The proposed R34 supplement feasibility project will lay the groundwork for a large RCT of the *Active Brains vs. Active Brains-Fitbit* vs attention placebo control HEP, and will help us understand whether the Fitbit is feasible and necessary to comprehensively improve function. Consistent with prior theory within a subsequent efficacy trial we will test the hypothesis that the *Active Brains-Fitbit* will be superior to the *Active Brains* and *HEP* in improving and sustaining improvements in objective, performance based and self-

reported physical and emotional function in older adults with heterogeneous chronic pain comorbid with MCI or MRP. Using the supplement to the NCCIH R34 mechanism we will follow an iterative design to adapt and refine both the (GetActive and GetActive with Fitbit) interventions to maximize feasibility, acceptability, credibility, recruitment protocol, adherence and measurements for patients with heterogeneous chronic pain. To allow objective measurement of activity in both *Active Brains* and *Active Brains-Fitbit* groups, we will use Accelerometer DMDs for 1 week at baseline and post-test. The Fitbit will be used to address/reinforce activity consistent with an individualized pacing plan, and to assess daily activity during the program only for those in the *Active Brains-Fitbit*. All procedures have already been piloted within our NCCIH R34 and will easily be adapted for the supplement.

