Aim 2: We will conduct 2 nonrandomized open pilots (30 patients total, 15/arm) of the refined *Active Brains-Fitbit* versus the refined Active Brain for patients with chronic pain and MCI or MRP. We will collect quantitative survey and exit interview data about feasibility, acceptability, and credibility. We will also compare the credibility, feasibility, usability and adherence between the 2 treatments as well as all study procedures in preparation for an efficacy trial.

Specific aims for phase III are:

Aim 3: We will conduct a virtual randomized controlled trial of the Active Brains-Fitbit program versus an education control (Health Enhancement Program) in chronic pain patients with MCI or MRP (N = 40 total; 5-8/group). We will collect quantitative survey and exit interview data about feasibility, acceptability, and credibility. We will use data to further refine the programs. We will compare the credibility, feasibility, usability and adherence between the two programs, *Active Brains-Fitbit* and the HEP, as well as all study procedures in preparation for an efficacy trial.

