*End of phase 1 deliverables: 1) develop the Active Brains and Active Brains-Fitbit through adapting GetActive and GetActive with Fitbit interventions/manuals to address the needs of patients with MCI or MRP); 2) identify/problem solve potential barriers to adherence to homework and Fitbit use during the duration of the program, and Accelerometer use for baseline and posttest assessments, including acceptability, credibility, feasibility, recruitment and adherence; 3) solidify inclusionary and exclusionary criteria and 4) finalized instruments to use in phase 2. We will use “lessons learned” from the year 1 activities of the R34 (focus groups and open pilot groups) to facilitate activities in phase 1. At the end of this phase we will have 2 interventions: Active Brains (GetActive adapted for MCI) and Active Brains-Fitbit (GetActive with Fitbit adapted for MCI).*

Phase II:

After enrollment, participants will be asked to attend one of the two intervention groups, *Active Brains* or *Active Brains-Fitbit* (N=30) in an open pilot. Participants will have either a choice of either the *Active Brains* or *Active Brains-Fitbit* one group is full; the remaining participants will then be assigned to the available group. The intervention groups will be conducted in person at MGH by trained study therapists over 10 weeks. Participants will complete demographic questions, baseline psychological and behavioral questionnaires, a cognitive assessment administer by a trained study staff, and an exit interview. Interview domains will include: 1) satisfaction with the intervention, 2) areas that were most helpful, 3) areas that were least helpful, 4) ways to improve the intervention and its acceptability (e.g. satisfaction, fit of the intervention within daily life, confidence in treatment and therapist), 5) perceived increase in self-report, objective and performance function.

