Aim 1. We will report feasibility as number of screened, eligible participants, and enrolled participants, and number of participants who completed at least 6 out of the 8 sessions. We will also report information on preliminary acceptability from quantitative and qualitative data, as well as information on credibility of intervention and adherence to DMD and Active Brains homework. We will also calculate descriptive statistics for quantitative measures. Qualitative Data Analyses: The qualitative focus group data and individual exit interview data will be transcribed and analyzed, using NVivo 10 qualitative software, and we will conduct thematic content analysis using guidelines provided by Miles and Huberman (1984)⁹⁹. The 2 coders (study clinician and research assistant) will meet on an ongoing basis with [name] to discuss the structural thematic framework, categories, and coding plan. To ensure coding reliability, coding discrepancies will be resolved through discussion and comparison of raw data. Coding will continue until a high reliability (Kappa= >0.80) is established. Once these data analyses are completed, the multidisciplinary team will provide the expert review of data, to discuss the interpretation of our findings in the context of current research on chronic heterogeneous pain. The same method was used successfully in our R34 grant.

Aim 2. To test in a small RCT pilot (N = 60 participants, 6 groups, 30/arm) the refined Active Brains with Fitbit versus Active Brains using the final adapted treatment manuals in preparation for a large RCT. We will report comparatively feasibility, credibility, acceptability and adherence between the 2 treatments. Feasibility will be assessed as depicted in the prior section. We will calculate the proportion of patients who complete at least 6 of the 8-planned treatment sessions (75%), along with the 95% confidence interval (CI) around this discontinuation rate. Treatments are considered feasible if over 70% of participants complete at least 6 treatment sessions. Adherence to treatment manual: We will assess adherence to treatment by listening to the audio recorded sessions, completing and analyzing the therapist adherence checklists. We will also rate adherence of study clinician in phase 2. The therapists will also

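### Phase II compares two programs filled by participant choice and then by leftover places, so differences between them cannot be attributed to the Fitbit, and the SAP still describes this contrast as randomised

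*Protocol*

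**What the plan says.** Protocol, II. Specific Aims, Phase II (Aim 2) sets the design: "We will conduct 2 nonrandomized open pilots (30 patients total, 15/arm". The same aim adds: "We will also compare the credibility, feasibility, usability and adherence between the 2 treatments".

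Protocol, Study Procedures, Phase II gives the allocation rule. It begins "Participants will have either a choice of either the", names the two programs, and says that when one group is full "the remaining participants will then be assigned to the available group". The sentence seems to have lost a connecting word. Choice first and assignment to the open group afterwards is the only workable reading.

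Phase III (Aim 3) is a "virtual randomized controlled trial of the Active Brains-Fitbit program versus an education control (Health Enhancement Program"; it has no arm that receives Active Brains without the Fitbit.

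Protocol, 3.1 Procedures Overview says that the project "will help us understand whether the Fitbit is feasible and necessary to comprehensively improve function". The SAP's Statistical Design and Power section carries nearly the same sentence.

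Protocol, V. Biostatistic Analysis covers qualitative coding and the handling of Fitbit data for Phases II and III. It does not mention recording preference, adjusting for it, or limiting how the Phase II comparison may be read.

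The SAP, Analyses plan, Aim 2, describes the contrast differently: "To test in a small RCT pilot (N = 60 participants, 6 groups, 30/arm) the refined Active Brains with Fitbit versus Active Brains". It plans to report the two treatments comparatively, and it excludes efficacy analyses.

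**The concern.** Credibility, adherence, usability and session completion are outcomes that wanting a program can plausibly move. If one program is filled by people who asked for it, and the other partly by late enrollees who had no choice, the scores can differ with no Fitbit effect at all. Two things are mixed into the comparison: the kind of person who prefers a Fitbit, and the effect of getting what one asked for. Enrolment order adds a third, because everyone placed without a choice enrols late and lands in the same program.

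Within the protocol, this is the only contrast between having and not having the Fitbit, so it is the only quantitative between-group evidence a reader could set beside the statement about necessity in 3.1. The SAP's comparative wording was written for randomised arms of 30. In the protocol the corresponding comparison is applied to self-selected groups of 15.

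**Working it through.** **1. The SAP's own figure.** The SAP states 80% power to confirm feasibility of each delivery modality, with N = 60 (30 per arm), true completion 77% and a threshold of 70%. The chance that one arm's observed rate exceeds 70%, by normal approximation, is Φ((0.77 − 0.70)/√(0.77 × 0.23/30)) = Φ(0.07/0.0768) = 0.82, close to the stated figure. The exact binomial gives 0.76 for at least 22 of 30 and 0.87 for at least 21 of 30. The stated power therefore concerns one arm against a fixed threshold. It is not a between-arm power, and it refers to 30 per arm. At the protocol's 15, the same rule (at least 11 of 15) gives 0.75. The protocol states no power or precision for the Phase II comparison.

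**2. Sampling error of the comparison at 15 per program.**
- Difference in completion, with an assumed 75% in both programs: 1.96 × √(2 × 0.75 × 0.25/15) = 0.31. At the SAP's 77% it is 1.96 × √(2 × 0.77 × 0.23/15) = 0.30.
- Difference in a mean score, in SD units: 1.96 × √(2/15) = 0.72.

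These half-widths would be the same under randomisation. They say nothing about preference bias.

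**3. How the allocation rule separates the groups.** The documents give no preference shares and no effect of preference, so the following only illustrates the mechanism. Thirty patients enrol in sequence and each prefers the Fitbit with an assumed probability q. Each gets the preferred program until one group reaches 15, and the rest go to the other group (20,000 simulated runs).

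| Assumed q | Prefer Fitbit, Fitbit group | Prefer Fitbit, Active Brains group | Placed without a choice (of 30) |
|---|---|---|---|
| 0.5 | 93% | 7% | about 4 |
| 0.7 | about 100% | 40% | about 9 |
| 0.9 | 100% | 80% | about 13 |

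Suppose people who prefer the Fitbit complete more often by an assumed 10 to 30 points, whichever program they receive. The spurious difference is the imbalance times that shift:
- q = 0.5: (0.93 − 0.07) × 10 to 30 = about 9 to 26 points
- q = 0.7: (1.00 − 0.40) × 10 to 30 = 6 to 18 points
- q = 0.9: (1.00 − 0.80) × 10 to 30 = 2 to 6 points

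Suppose instead that receiving one's preferred program adds 10 to 30 points. The share matched is then 93% against 93% at q = 0.5 (difference 0), 100% against 60% at q = 0.7 (4 to 12 points), and 100% against 20% at q = 0.9 (8 to 24 points).

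The two mechanisms rank the scenarios in opposite order. The size of the bias therefore cannot be fixed from the documents, and a larger sample would not reduce it.

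**4. Which design governs.** The SAP is dated June 1, 2018. The protocol describes a virtual Phase III and cites a 2020 validation study of the mobile walk test, so it appears to be later and its non-randomised Phase II appears to be operative. On that reading the protocol (15 per program, by choice) and the SAP (30 per arm, randomised) describe different studies under Aim 2.

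**The case against.** The strongest reply is that the protocol is open about the design. It calls these pilots non-randomised, and describing two pilots side by side is ordinary practice. The SAP judges completion against a fixed 70% threshold, reports percent change within each group, specifies no between-arm test and rules out efficacy analyses. Section 3.1 itself calls the project groundwork and leaves the superiority hypothesis to a later efficacy trial. All of this is correct, and feasibility results within each program are unaffected. It does not withdraw the comparison stated in Aim 2 or the wording about necessity, and nothing in either document limits how a difference between programs may be read.

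Four stronger readings are tempting, and the documents do not support them:
- *Phase II will decide whether the Fitbit stays in the future trial.* No passage gives such a rule. Both documents already name both programs as arms of that trial. The stated use of the Phase II interview, satisfaction and credibility data is to refine the intervention.
- *Every participant chose their program.* Late enrollees are assigned to the group that has room.
- *No randomised Fitbit contrast appears anywhere.* The SAP describes one. If that design governed, the preference confounding would not arise.
- *The half-widths of 31 points and 0.72 SD measure the bias.* They measure sampling error only.

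**Conclusion.** The concern holds for Phase II as the protocol describes it. A difference in credibility, feasibility, usability or adherence between the two programs is confounded with preference and enrolment order, and it cannot support the claim that the Fitbit is necessary. No analysis plan matches this design, because the SAP still describes an RCT with 30 per arm. The bias has no size that the documents can supply. Separately, sampling error at 15 per program is about ±31 percentage points for completion (assuming rates near 75%) and ±0.72 SD for a mean score, by normal approximation.

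The conclusion assumes that the protocol is the operative document. Under the SAP's design the confounding would go, but at 30 per arm the half-width for completion would still be 1.96 × √(2 × 0.77 × 0.23/30) = 0.21, and with efficacy analyses excluded necessity would still not be shown. This is an inexpensive correction that should be made; the pilot's feasibility purpose is intact.

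**What to change.** 1. In Protocol, II. Specific Aims, Phase II (Aim 2), and in SAP, Analyses plan, Aim 2, replace the between-treatment comparison for Phase II with results for each program separately: estimate and 95% CI, with completion judged against the existing 70% threshold. State that differences between programs are not attributed to the Fitbit.
2. Record each participant's preferred program at enrolment, before group availability is disclosed, and whether they received it. Describe credibility and adherence by preference. A simple chose-or-assigned flag is not enough: everyone assigned falls in one program, and an assigned participant may have wanted that program anyway.
3. In Protocol 3.1 and in SAP, Statistical Design and Power, delete the words *and necessary*, or state that necessity is left to the future randomised three-arm trial.
4. Reconcile the SAP's description of Aim 2 as an RCT of 60, and its reference to randomised participants in the design section, with the protocol's Phase II aim and procedures.

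The cost is wording in both documents and two short enrolment items, with no change to sample size or treatment. The pilot gives up a between-program comparison that it could not support, and the preference subgroups will be small and descriptive only. If Phase II enrolment is already over, preference can no longer be collected prospectively, but items 1, 3 and 4 still apply.

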### III. SUBJECT SELECTION

Participants will be recruited among patients with MCI or MRP and chronic pain who present to the Memory Clinic or the Pain Clinic at the Massachusetts General Hospital or PAC and meet study criteria. We have support from the Memory Clinic and the Pain Clinic with recruitment, and have budgeted research assistant time to facilitate enrollment on site. Physicians will first inform the eligible patients (with MCI or MRP and chronic pain) about the study and give them study flyers. Participants will be new patients presenting to Partners-affiliated medical practices for memory or pain, or patients presenting to Boston area pain and memory centers and medical practices that treat chronic pain patients and meet study criteria. Participants may hear about the study from Rally or recruitment flyers with tear-off research coordinator contact information that will be posted in the hospital and at referral sites. Our IRB approved flyers will also be posted to memory related groups (e.g. open forums for MCI, Facebook groups for individuals with memory problems and their loved ones) online. We will post to publicly accessible groups, as well as moderated groups. We will review and comply with group guidelines prior to posting our study advertisement. A research assistant will reach out to the participant by phone or by email. A research assistant will provide study details to interested participants and screen for eligibility; those who wish to participate will complete the informed consent process. Participants will be asked to self-report if they have any memory problems, such as problems forgetting names, events, getting lost, or having to re-read information over and over. If necessary, we will also ask if others have noted that the participant has had these challenges. (Phase I only): We will first recruit patients and then ask if they have a caregiver that may be willing to participate. If the patient is referred in-clinic, we will only contact the caregiver if the patient gives permission. Patients without a caregiver are still eligible to attend the focus groups. Caregivers have the opportunity to contact the study staff through our Rally advertisement. Caregivers without a patient (e.g. patient screens out) are still eligible to attend the focus groups. These procedures will be done in a private setting, and will not impact in any way the delivery of care within the practice. This strategy has been used successfully in prior studies conducted by the PI. Subjects will be older adult

(age 60 or older) patients with a MCI or MRP, who also have chronic pain (pain present for 3 months or longer). Caregivers will only be recruited during Phase I.

Recruitment will also occur through the Research Patient Database Registry (RPDR). The RPDR is a centralized clinical data registry that gathers data from various hospital legacy systems and stores it in one place. Researchers access the data using the RPDR online Query Tool. They may query the RPDR data for aggregate totals, and with proper IRB approval, obtain medical record data. The RPDR ensures the security of patient information by controlling and auditing the distribution of patient data within the guidelines of the IRB and with the use of several built-in, automated security measures. To identify potentially eligible patients:

- 1) A RPDR query will be performed to identify those patients with chronic pain diagnoses. Study staff will review the medical record to confirm potential participant eligibility and to identify their linkage to an MGH primary care physician. Access to patients' medical records will be restricted to this pre-enrollment recruitment phase.
- 2) Study staff then will obtain permission for initial contact from each potentially eligible patient's PCP by having providers review letters and discard ones that they do not approve.
- 3) For physician-approved patients, study staff will send a study introduction letter from the patient's physician (with the clinician's name at the bottom) and a study opt-out letter signed by [name] (PI). The letter from the PCP informs the patient that he or she is allowing the study to contact patients with chronic pain in case they are interested in learning about the study. [name] letter is an opt-out letter describing the study, the procedure to opt out of further contact, and whom to call for further information.
- 4) Should study staff receive no reply within 10 days, staff members will call the patient on the phone to assess interest in the study and to describe the study over the phone. If the patient remains interested, staff will confirm eligibility and assess for inclusion and exclusion criteria.
- 5) For potentially eligible patients who are enrolled in the MGH Research Options Direct to You (RODY) Program, we will send them an opt-out letter and call 10 days later to inform them about the study. RODY identifies patients who are willing to be contacted directly about research studies. Patients who have agreed to be contacted directly are identifiable through the RPDR search; each patient's RODY status is available in the demographics table included in the RPDR output.

A research assistant will provide study details to interested participants and screen for eligibility; those who wish to participate will complete the informed consent process. These procedures will be done in a private setting over the phone, and will not impact in any way the delivery of care within the practice. This strategy has been used successfully in prior studies conducted by the PI. Data will be collected in MGH Integrated Brain Health Clinical and Research Program and will be managed and analyzed collaboratively by investigators at MGH.

**4. Feasibility** The Memory Clinic at MGH is a busy clinical and research practice. The Center has approximately 498 patients with MCI who are seen yearly for care. Of these, approximately 50% are chronic pain patients. As such, we can be confident that we will be able to identify and recruit the necessary number of participants. However, if any recruitment difficulties occur, we will be able to recruit participants from Brigham and Women's Hospital's Memory Clinic.

#### IV. SUBJECT ENROLLMENT

Interested participants who meet study criteria will be consented and then scheduled to participate in one of the focus groups (in Phase I) or intervention groups (in Phase II). See Table 1.

Table 1	
Patient Inclusion Criteria	Rationale
Male and female outpatients, age 60 years or older	Population under study
Have nonmalignant chronic pain for more than 3 months	International Association for Study of Pain (IASP)  criteria

Has MCI or memory-related problems (MRP) (forgetting names, getting lost, forgetting obligations)	Population of study
Able to perform a 6-minute walk test at an accelerated pace	Program will involve increase number of steps/outcome measure
Free of concurrent psychotropic or pain medication for at least 2 weeks prior to initiation of treatment, OR stable on current psychotropic or pain medication for a minimum of 6 weeks and willing to maintain a stable dose	Treatment confound
Cleared by a medical doctor for study participation	Human subject concern, risk
Owns a smartphone with Bluetooth 4.0	Necessary for pairing with DMD and storing/downloading data.
Caregiver Inclusion Criteria (Phase I only)	Rationale
Caring for someone with mild cognitive impairment and chronic pain	Population of study
Currently living with someone with mild cognitive impairment and chronic pain	Population of study
Patient Exclusion Criteria	Rationale
Diagnosed with a medical illness expected to worsen in the next 6 months (e.g., malignancy)	Treatment confound
Serious mental illness or instability for which hospitalization may be likely in the next 6 months	Feasibility, participant safety
Current suicidal ideation reported on self-report	Subject safety
Lifetime history of schizophrenia, bipolar disorder, or other psychotic disorder	Treatment confound
Current substance abuse or dependence and current substance use disorder, within the past 6 months	Treatment confound
Practice of yoga/meditation, or other mind body techniques that elicit the RR, once per week for 45min or more within the last 3 months or less	Treatment confound
Regular use of Fitbit in the last 3 months.	Treatment confound
Engage in regular intensive physical exercise for more than 30 minutes a day	Treatment confound
Unable to walk without use of assistance (e.g. walker, cane, wheelchair)	Treatment confound

